3.5 Sample size calculation

This sample size is likely to be achievable given the expected number of cases that will be available in the clinics employed in this proposal. Retrospective data available from the School Dental Service, Health Promotion Board showed that RET treatment was provided to 78 patients (with 85 teeth) over a period of 3 years 6 months (Mar 2009 to Dec 2012). 77.2% of these teeth were mandibular premolars, 13.9% were maxillary incisors, and 8.9 % were maxillary premolars. Of these, 69.4% (n=59) had successful outcomes with closed apices following RET treatment, 7.1% (n=6) showed signs of increased root length and dentine wall thickening but were still undergoing review, 5.9% (n=5) did not show signs of root growth but demonstrated resolution of periapical pathology, 8.2% (n =7) had unfavourable outcomes with apices remaining open and signs of periapical pathology, and 9.4% (n=8) were loss to follow up.

The proposal will be for a sample size of 30 teeth per group, i.e. total estimated recruitment is 60 teeth. The sample size proposed is calculated based on data obtained from a published paper by Bose et al (2009). The sample size is estimated based on changes in root length as the primary outcome measure. Using a 2-sided sample test, assuming a mean difference between the groups of 1.5 and SD of 2, (at a significance level of 0.05 and 80% power), the sample size required is 30 subjects per group, i.e. 60 subjects in total. It is our hope that a multi-centre approach will help increase the caption group and thus increase patient numbers.

This is in agreement with sample size proposed in existing on-going randomized control trials which are registered on the Clinical Trial database website: www.clinicaltrials.gov. The clinical trials have similar age-range of potential patients as the proposed study.

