This also begs the question if antibiotics are truly a necessary and beneficial component in the preparation for a sterile root canal. Prior laboratory in-vitro studies have determined that disinfection protocols have a profound effect on stem cells of the apical papilla (SCAP) as well as dentine microhardness. Yassen et al demonstrated that dentine microhardness was significantly reduced when triple or double antibiotic mixtures were used for treatment of dentine compared to Ca(OH)_2 (20). Antibiotic paste formulations used in RET procedures were found to be directly toxic to stem cells even at concentrations as low as 1% of doses currently used in treating patients, while conversely dentin conditioning with Ca(OH)_2 was found to promote SCAP survival and proliferation (21, 22). This may well have clinical implications impacting fracture resistance and SCAP survival in immature permanent teeth with already compromised root thickness.

Given that this procedure (Regenerative Endodontic Therapy using revascularization via blood clotting method) has been carried out in children in Singapore since 2007, and a retrospective study is in progress, it is considered timely to conduct a prospective randomized controlled study to evaluate the need for antibiotic pastes and the outcome and success of RET.

2.0 Research questions/Aims and Objectives:

Research questions:

1. Are there differences between treatment outcomes of a 2-Mix antibiotic paste (Ciprofloxacin and Metronidazole) vs disinfection with the currently accepted multiple-visit protocol in non-surgical root canal treatment (i.e. disinfection with NaOCl solution followed by Ca(OH)₂ as inter-appointment dressing) with respect to:
 - i. Resolution of apical periodontitis.
 - ii. Thickening of dentinal walls and/or continued root development with or without apical closure.
2. Which are the baseline characteristics which could predispose a case to successful outcome?
3. Will discolouration of teeth occur and to what extent?

Primary aim

1. To assess frequency of periapical healing in the two sets of experimental protocols.
2. To study the differences in qualitative and quantitative increase in root dimensions of different protocols, by evaluating continued root development and thickening of dentinal walls.

Secondary aims

1. To evaluate if tooth discolouration occurs by evaluating the changes in tooth colour following treatment using the different protocols.

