3.4.2.3 Review visits and parameters for evaluation of clinical outcomes

The primary purpose of review appointments is to assess healing and continued root development. Patients will be reviewed according to the set protocol stated above. Each tooth will be accounted for as an individual case, regardless of whether it originates from the same patient or not. Data will be recorded into a data collection sheet (**Appendix F**) and transferred into an Excel spreadsheet prior to analysis.

During the review visits, the following outcomes will be assessed:

Clinical-

- Presence/absence of tooth
- Mobility
- Periodontal probing (6 point evaluation for pocket depth)
- Tenderness to percussion and palpation
- Percussion note
- Free from pain or discomfort
- No evidence of labial swelling or abscess, signifying continued presence of infection
- Presence of discolouration

Radiographic

Standardised periapical radiographs will be taken before the start of treatment, at the end of the treatment and then again at each recall visit post treatment. Final outcome measures will be recorded at the 18th month review. This protocol is a standard clinical protocol and no additional radiographs will be taken for the purposes of this study.

A standardized beam aligning holder for both direct and indirect sensors will be utilized during taking of radiographs. All radiographs will be evaluated for periapical status and qualitative and quantitative status of root dimensions.

Standard Pulp Sensibility Tests

At each recall, pulp sensibility responses will be evaluated using thermal test (EndoIce) and Electric Pulp Test (EPT). Evaluation of tooth mobility, tenderness to percussion and palpation will also be carried out. This procedure will be done at the baseline, and during each subsequent review visit following completion of treatment.

Photography

Standardized intra-oral photographs will be taken before the start of the treatment and each recall visit. Post treatment crown colour in comparison to the pre-operative photographs and to that of the contralateral tooth will be assessed using the MathWorks software as described in the study by Day et al

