3.4.2.4 Radiographic Analysis

Measurements of digital radiographs will be carried out using the measurement tool available in the VixWin digital radiography viewing software. Calibration of the measurements (based on the known width of the digital film) will be done prior to carrying out of quantitative measurements. Digital radiographs will be read in a darkened room, on a standardized monitor (DELL E2213H 1920 x 1080 Pixel Resolution 22" LCD Display) screen and computer with Windows Operating System (OS).

For length measurements, the point of reference will be the cement-enamel junction (CEJ) and Measurement ideals are referenced from the article by Bose *et al*(10), Chugal *et al* 2001(25) and Yu *et al* 2012(26). Below are the set definitions and proposed criteria which will be used for measuring the abovementioned parameters for radiographic analysis:

1. Size of periapical lesion,
 - Measured using the periapical index (PAI) scoring system (27)
2. Resolvement of periapical lesion;
 - Defined as the complete absence of existing periapical radiolucency as compared with pre-operative radiograph
3. Root length

- Quantitative outcome: Measured in millimeters (mm) as a straight line from the CEJ to the radiographic apex of the tooth;
- Binary outcomes: Comparison of increase in root length (Yes/No)
- Both pre and post-operative (measured during the recall visits) will be recorded.

4. Dentinal wall thickness measurements (at apical and mid root)
 - Quantitative outcome: Measured in millimeters (mm) at the apical one third of the tooth;
 - Binary outcomes: Comparison of increase in dentine wall thickness (Yes/No)
 - The dentinal wall thickness for both the preoperative and recall images will be measured at the level of the apical one third of the preoperative root canal length measured from the CEJ. The root canal width and the pulp space will be measured at this level, and the remaining dentin thickness will be calculated by subtracting the pulp space from the root canal width
5. Width of apex;
 - Measured in millimeters (mm) as the distance between the inner sides of the open apex
 - Binary outcomes: Comparison of decrease in width of apex (Yes/No)
6. Continued root development;
 - Measured as Postoperative root length minus Pre-operative root length (in millimeters) (mm); percentage change will also be calculated
7. Closure of apex;
 - Measured by means of visual identification; defined as approximation of the inner sides of the root tips.

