4.5. Statistical methods

All analysis will be carried at a tooth level, where each tooth will be accounted for as an individual case. Descriptive statistics (both discrete and non-discrete variables), which will include means, standard deviations, frequencies and percentages will be determined. Data will be checked for homogeneity of variance prior to application of statistical tests. Appropriate correlation and regression analysis will be

employed in consultation with a biostatistician. Inter and intra-operator variability scores will be evaluated using Kappa statistics. The significance level will be set at $p<0.05$. All data will be analyzed using SPSS Statistical Package (IBM SPSS Statistics).

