6.2. Ensuring patient return for reviews

As this is a randomized controlled clinical study, it is possible that patients may not return for recalls following completion of procedures, resulting in drop outs. As such, a 10% margin for drop outs has been assumed in the power calculation. Intention to treat analysis will also be carried out.

Patients enrolled in the study will be followed up closely, and appointments at appropriate intervals as specified in the protocol will be made. Patients will be reminded to attend the review visits 2 days in advance via telephone or SMS. Treatment rendered and review visits will not be charged.

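### Section 2.0 makes periapical healing and root dimensions both primary, but section 3.5 names and sizes only root length, and nothing ranks the measures

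*Protocol*

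**What the plan says.** Section 2.0 of the protocol has two items under its primary aim heading and does not rank them. The first is "To assess frequency of periapical healing in the two sets of experimental protocols". The second concerns increase in root dimensions, to be studied "by evaluating continued root development and thickening of dentinal walls".

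Section 3.3 lists healing first and root measurements second, and marks neither as primary. Section 3.4.2.3 adds that "The primary purpose of review appointments is to assess healing and continued root development", and that "Final outcome measures will be recorded at the 18th month review".

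Section 3.5 is the only place that names a primary outcome: "The sample size is estimated based on changes in root length as the primary outcome measure". It assumes a difference of 1.5, an SD of 2, two-sided 0.05 and 80% power, and arrives at 30 per group. It contains no calculation for healing or wall thickness.

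Section 3.4.2.4 defines continued root development as root length change ("Measured as Postoperative root length minus Pre-operative root length") and treats dentinal wall thickness as a separate measurement. Section 4.5 gives one significance level, 0.05, for everything.

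**The concern.** Root length belongs to the second primary aim, so section 3.5 does not introduce a foreign outcome. It narrows the second aim to one component and passes over the first aim altogether. A reader of section 2.0 would count healing and wall thickness as primary; a reader of section 3.5 would not.

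Two things are at stake. First, once results are known, a significant difference in healing, root length or wall thickness could each be presented as success on a primary objective, with support in the text. Second, section 8.0 hopes to show that antibiotics are unnecessary for success in this treatment. A non-significant healing result labelled primary could be offered as evidence for that, although the trial was never sized for healing.

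**Working it through.** **1. The plan's own figure.** Inputs from section 3.5: difference 1.5, SD 2, so d = 1.5/2 = 0.75; two-sided α = 0.05; power 80%.

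- Normal approximation: n = 2(1.960 + 0.842)²/0.75² = 27.9, so 28 per group.
- Two-sample t-test: 28.9, so 29 per group.
- Power at 30 per group (t-test): 81.5%.

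The stated 30 therefore reproduces for root length. Section 6.2 says "a 10% margin for drop outs has been assumed in the power calculation"; with 10% lost, 30 × 0.9 = 27 per group remain and power is 77.2%.

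**2. False-positive risk if each measure may count as primary at 0.05.**

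| Measures | Independent | Correlation 0.5 | Correlation 0.8 |
|---|---|---|---|
| Two | 1 − 0.95² = 9.75% | about 9% | – |
| Three (healing, length, wall thickness) | 1 − 0.95³ = 14.3% | about 12.5% | 9.8% |

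The correlated figures come from simulating 2,000,000 sets of equally correlated normal statistics. The correlations are assumptions.

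**3. Power for healing.** The protocol gives no planning rate. The retrospective counts in section 3.5 suggest a range: 59 + 6 + 5 = 70 teeth were neither unfavourable nor lost, so 70/85 = 82% of all teeth, or 70/77 = 91% of those followed. Treating all 70 as healed is an assumption that the protocol does not state. The 20-point gap is also assumed. Exact power at two-sided 0.05:

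| Healing rates | Test | 27 per group | 30 per group |
|---|---|---|---|
| 82% v 62% | Fisher | 26.9% | 31.0% |
| 82% v 62% | Chi-square | 39.3% | 40.8% |
| 91% v 71% | Fisher | 32.0% | 38.2% |
| 91% v 71% | Chi-square | 50.3% | 51.9% |

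For 80% power at 27–30 per group, the gap must be about 30–36 points (chi-square) or 34–40 points (Fisher).

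**4. Cost of keeping two primary outcomes.** With two outcomes, the first Holm step uses 0.05/2 = 0.025.

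- Root length at 0.025: power 72.6% at 30 per group and 67.3% at 27. For 80% power n = 35.1, so 36 per group before dropout.
- Healing, 20-point gap, 80% power, normal approximation with pooled variance under the null: 60 (91% v 71%) to 78 (82% v 62%) per group at 0.05, and 72 to 95 at 0.025.

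**The case against.** The strongest reply is that aims are not outcomes. A trial may pursue two primary aims and size itself on one measure, and section 3.5 is the only place that names a primary outcome. The sentence in section 3.4.2.3 explains why visits are held and does not designate an endpoint. Test order and allocation of α often sit in a statistical analysis plan, which is not available here.

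Much of this is fair. Section 3.4.2.3 is supporting text only, and the lack of an α rule would be a weak point by itself. The false-positive figures apply only if no later document ranks the measures. But an analysis plan would inherit two different statements of what is primary, and choosing the primary outcome is the protocol's job.

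The healing figures are also open to challenge. The rates are inferred, and 20 points is one choice among many. Section 3.4.1 admits some teeth with no radiographic lesion, whereas section 3.4.2.4 defines resolution relative to an existing one, so the healing denominator may be below 27–30 per group and power lower still. The figures illustrate the problem and are not bounds; the conflict in the text does not depend on them.

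Finally, the 36 per group for root length under Holm is a worst case: if healing is rejected first, root length may be tested at 0.05.

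**Conclusion.** The concern holds. Sections 2.0 and 3.5 disagree on whether healing and wall thickness are primary, and no other section settles it. This should be corrected before results are seen; it does not undermine the design, because the sizing for root length is sound at 30 evaluable teeth per group (81.5% power) and slightly short at 27 (77.2%).

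Left as it is, the protocol permits an error rate of up to 14.3% across three independent measures, on the assumption that each is tested at 0.05 and any may be claimed. For healing, the planned size can reliably detect only gaps of roughly 30–40 points under the assumed 82–91% rate, so a null result there would be weak evidence that the two dressings are equivalent.

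**What to change.** **Preferred.** In sections 2.0, 3.3 and 3.5, name one primary outcome: change in root length in mm from baseline to the 18-month review. Make periapical healing and dentinal wall thickness secondary, reported with 95% confidence intervals and no confirmatory claim. Bring the sentence on the purpose of reviews in section 3.4.2.3 into line. This is a wording amendment with no added patients; the price is that healing, now the first-listed aim, loses its primary label.

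**Alternative.** If the sponsor regards healing as scientifically primary, keep healing and root length as two primary outcomes, apply Holm across them, make wall thickness secondary, and restate the sample size for both with a justified healing rate and difference. This is not a wording change: at 0.025, root length needs up to 36 per group before dropout, and a 20-point healing difference about 72–95 per group under the assumed rates, against 30 planned.

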4.0 Randomization

4.1. Sequence generation

It is proposed that the randomization process will be generated by a Biostatistician. A blocked randomized sequence will be used to generate a randomized sequence for each of the centres.

4.2. Allocation concealment and implementation

Randomization codes will be held by the delegated study team member, who will convey the randomization allocation to the operator. The delegated study team member (randomization code holder) will be responsible for maintaining the allocation log, and will inform the investigator of the assigned randomization ID as well as the intervention group assigned to the patient. (**Appendix E - Patient ID and Intervention Allocation and Log Documentation Workflow**). The study team member who will perform the randomization will be trained and will be delegated in the responsibility log.

Materials to be used in both groups will be made available at each recruitment site. Potential participants must firstly be assessed for eligibility, be recruited and consented, after which only can the randomization codes be accessed.

4.3 Blinding and Unblinding protocol

The participants and the assessors (blinded team) for treatment outcomes will be blinded to the intervention used.

Unblinding will be done under the circumstances that any Serious Adverse Events (SAE) occurs during the course of the study, e.g. allergic reaction following administration of Investigational Product (i.e. antibiotics or Ca(OH)₂). All SAE or Unanticipated Problem Involving Risks to Subjects or Others (UPIRTSO) events will be logged and reported accordingly.

Unblinding Protocol: Unblinding envelopes containing the codes will be kept at the individual sites. In the event that unblinding will need to be carried out, the PI will access the codes to verify the investigational product used in the treatment.

4.4. Safety Reporting Guidelines

A serious adverse event (experience) or reaction is any untoward medical occurrence that at any dose:

- results in death,
- is life-threatening,
- requires inpatient hospitalisation or prolongation of existing hospitalisation,
- results in persistent or significant disability/incapacity, or

Time frame and procedures for reporting of SAE to HSA will be in accordance to that specified by the Health Sciences Authority Health Products Regulation Group (Version June 2011).

For reporting of Unanticipated Problem Involving Risks to Subjects of Others (UPIRTSO), the following 2 criteria have to be met:

(A) Unexpected – Where in terms of nature, severity of frequency is not consistent with:

- a. Research procedures described in the protocol related documents
- b. Characteristic of subject population studied

(B) Related – where there is reasonable possibility that the incident, experience or outcome may have been caused by the procedures involved in the research

UPIRTSO reporting timeline for event:

1. Urgent Reporting: All problems involving local deaths, whether related or not, will be reported within 24 hours after first knowledge by the PI
2. Expedited Reporting: All other problems will be reported as soon as possible, but not later than 7 calendar days after first knowledge by the PI
3. HSA reporting requirements: The PI will inform HSA no later than 15 calendar days after first knowledge that the case qualifies for expedited reporting. The PI will be responsible for providing HSA with follow-up information and to submit it as soon as it becomes available.

4.5. Statistical methods

All analysis will be carried at a tooth level, where each tooth will be accounted for as an individual case. Descriptive statistics (both discrete and non-discrete variables), which will include means, standard deviations, frequencies and percentages will be determined. Data will be checked for homogeneity of variance prior to application of statistical tests. Appropriate correlation and regression analysis will be

employed in consultation with a biostatistician. Inter and intra-operator variability scores will be evaluated using Kappa statistics. The significance level will be set at $p<0.05$. All data will be analyzed using SPSS Statistical Package (IBM SPSS Statistics).

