3.2 Intervention: Study arms and Investigational Product (IP) used

Following canal debridement procedures, patients will be randomly assigned to receive different combinations of inter-appointment dressing, which will be one of the following:

- Experimental: Group A - Double Antibiotic Paste consisting of Ciprofloxacin and Metronidazole
Intervention named: 2-Mix Antibiotic Paste
- Experimental: Group B - Non-setting calcium hydroxide paste inter-appointment dressing, aimed at prevention of re-colonization of canal space.
Intervention named: Ca(OH)₂

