Informed consent from the parents and child assent will be obtained. **Appendix B (Participant Information Sheet with Main ICF) and Appendix C1-4 (Chinese, Malay, and Tamil Short Consent Form and Child Assent form).**

Participation in this study is purely voluntary. If either parents or patients are unwilling to participate in this study, they will not be recruited. Patients who wish to withdraw from the study may do so at any stage of the study. If the patient declines taking part in this study, the tooth will be accessed and dressed with $\text{Ca}(\text{OH})_2$ according to currently accepted treatment protocol for management of patients with non-vital immature permanent teeth followed by application of MTA and obturation with gutta percha.

The data required will be collected prospectively. All data will be collected and analyzed in a de-identified format, with each individual assigned a unique identification number. IRB approval will be obtained prior to commencement of the study.

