- The antibiotics will be placed into the root canal with a carrier and pluggers to completely fill the root canal system; Controls will be filled with Ca(OH)_2 , placed in according to currently employed procedures.
- The root canal will then be hermetically sealed with a sterile cotton pledge, IRM and a glass ionomer cement to prevent any coronal leakage or contamination of the root canal with oral microorganisms.
- The patient will then be discharged, and given an appointment to return for the next step of treatment in 4 weeks \pm 7 days.

Second Treatment Visit:

- The tooth will be examined and evaluated for clinical signs of an abscess, increased mobility and presence of the existing coronal seal restoration prior to commencement of local anaesthesia and rubber dam procedures.
 - If any of the above is present, a repeat session of disinfection is necessary and the first treatment visit procedures will be repeated until there is no clinical presence of an abscess or sinus tract. Information on number of additional disinfection visits will be recorded.
 - The operator/assistant will refer to patient ID recorded in treatment notes, and access the Intervention Log and double check the intervention group assigned to the patient prior to preparing the medicament to be used.
- Local anaesthesia without a vasoconstrictor will be administered and the tooth will be isolated and re-accessed as described above.
- The antibiotic mixture will be flushed out of the root canal by irrigation until solution runs clear with sodium hypochlorite. Ca(OH)_2 dressing will be removed by essentially the same procedure.
- The root canal will be irrigated slowly with 10ml 17% EDTA.
- Following this, the root canal will be thoroughly dried with paper points.
- A sterile 23-gauge needle or sterile file with a length of 25mm will be inserted beyond the working length and past the confines of the root canal into the periapical tissues to intentionally induce bleeding into the root canal. The bleeding is then allowed to fill the root canal.
- Once the root canal is filled with blood, a moist cotton pledge will be placed in the root canal below the cementoenamel junction (CEJ), and a clot will be allowed to form in the root canal.
- Once the clot is formed, the coronal portion of the root canal will be cleaned (with a new sterile cotton pledge moistened with saline) to remove any remnants of blood, which could cause discolouration in future

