5.0 Data management

5.1 Data storage

Any data collected on paper will be stored in a designated locked cabinet at the research site. Data will be entered into an OMR sheet for accuracy. All electronic data collected will be kept in a password secured portable computer and backed up to dedicated password protected local back-up drive every week.

Some measures may include password protection, security under lock and key, access controlled office, etc. To protect patient confidentiality, records and logs will be stored in locked file cabinets, in locked offices, and on computers protected by a password. A patient identification log will also be put in place - each patient's data will be coded with an identifier, and the key to the code will be located in another physical location or on a separate computer. All patient identification logs will be kept for 6 years, after which it will be securely disposed of. The data will only be accessible to the study team members involved in and approved for the study. Identifiers of participants (i.e. birth certificate numbers, date of birth, email addresses, mailing addresses) will be extracted and each patient will be allocated an individual number to secure patient's identity. All data will be kept for 6 years upon completion of study.

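### The arm is assigned to the patient, but every tooth is analysed as an individual case even within one child; if a child's teeth share the arm and correlate positively, standard errors would be modestly too small.

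*Protocol*

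**What the plan says.** **Allocation is described by patient.** Protocol 3.2 says that "patients will be randomly assigned to receive different combinations of inter-appointment dressing". In 4.2 the code holder gives the investigator the "assigned randomization ID as well as the intervention group assigned to the patient". At the second treatment visit (3.4.2.2) the operator or assistant is to "refer to patient ID recorded in treatment notes, and access the Intervention Log and double check the intervention group assigned to the patient". Identifiers are also one per person: "with each individual assigned a unique identification number" (3.4.2.1) and "each patient will be allocated an individual number to secure patient's identity" (5.1). No tooth-level code is described.

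**Analysis is described by tooth.** Section 4.5: "All analysis will be carried at a tooth level, where each tooth will be accounted for as an individual case". Section 3.4.2.3 goes further: "Each tooth will be accounted for as an individual case, regardless of whether it originates from the same patient or not". The only modelling statement is in 4.5: "Appropriate correlation and regression analysis will be" employed in consultation with a biostatistician. No patient cluster is named.

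**More than one tooth per child is possible.** The criteria in 3.4.1 set no limit of one tooth. The retrospective series in 3.5, from one of the trial's own sites, had 85 teeth in 78 patients.

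**The sample size uses both units.** Section 3.5 gives 30 per group once as teeth and once as subjects.

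**The concern.** Two teeth in one mouth share age, host response, oral environment and often the operator, so their outcomes may well be correlated. If they also share an arm, the second tooth adds less information about the treatment difference than a tooth from another child. A test that counts both as independent then has a standard error that is too small, a confidence interval that is too narrow, and a type I error above the 5% set in 4.5.

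This is not a detail left for an analysis plan. The protocol foresees several teeth from one child and directs that the link be disregarded, so a clustered analysis would have to depart from the wording of 3.4.2.3. The two units in 3.5 agree only if every child contributes exactly one tooth.

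**Working it through.** **1. The plan's own figure.** Inputs from 3.5: difference 1.5, SD 2, two-sided 0.05, power 80%. The normal formula gives n = 2 × (1.96 + 0.8416)² × (2/1.5)² = 27.9, so 28 per group; the exact t-test needs 28.9, so 29. The stated 30 is reproduced to within 2, but only for independent observations. Power at 30 independent teeth per group (noncentral t, d = 1.5/2 = 0.75) is 81.5%.

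**2. Cluster sizes (assumed from 3.5).** 85 − 78 = 7 extra teeth. If they come in pairs, 71 children have one tooth and 7 have two. Then Σm²/Σm = (71 × 1 + 7 × 4)/85 = 99/85 = 1.165. Scaled to 60 teeth this is 60 × 7/85 = 4.9, or about 5 two-tooth children.

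**3. Within-child correlation ρ.** Not given in the protocol; 0.1 to 0.8 is assumed.

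**4. Formulas, for teeth of one child in the same arm.**
- Design effect DE = 1 + (1.165 − 1) × ρ
- Correct SE / planned SE = √DE
- True alpha = 2 × [1 − Φ(1.96/√DE)]
- Effective teeth per arm = 30/DE, entered in the noncentral t power

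| ρ | DE | SE ratio | True alpha | Effective teeth per arm | Power |
|---|---|---|---|---|---|
| 0 | 1 | 1 | 5.0% | 30 | 81.5% |
| 0.1 | 1.016 | 1.008 | 5.2% | 29.5 | 80.8% |
| 0.3 | 1.049 | 1.024 | 5.6% | 28.6 | 79.6% |
| 0.5 | 1.082 | 1.040 | 6.0% | 27.7 | 78.3% |
| 0.8 | 1.132 | 1.064 | 6.5% | 26.5 | 76.4% |

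The power column is for a correctly sized test and applies only if 30 means teeth.

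**5. Simulation of the planned tooth-level t-test.** 60 teeth, 5 two-tooth children, patient-level allocation in assumed blocks of 4, 100,000 trials per cell, ρ = 0.1/0.3/0.5/0.8: alpha 5.1%/5.6%/5.9%/6.5%, in line with the table. With 2 two-tooth children it is 5.1% to 5.7%.

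**6. If each tooth took the next code instead.** Same setting, 5 two-tooth children: alpha 4.7% to 5.0%. The inflation disappears.

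**7. Which correction works (continuous outcome, 5 two-tooth children).**
- Cluster-robust test, small-sample corrected, t on (patients − 2) df: alpha 5.0% to 5.2% with a shared arm and 4.9% to 5.1% with tooth-by-tooth codes.
- Uncorrected sandwich with a normal reference: about 5.5% to 6.2% with a shared arm, so little is gained.
- Random-intercept REML: 4.7% to 5.1% with a shared arm, but about 6% to 9% with tooth-by-tooth codes (9% to 16% with only 2 two-tooth children).

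The binary-outcome version was not simulated.

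**The case against.** The strongest reply is that the direction of the error is not certain. The protocol does not separately say how a second tooth of the same child is allocated, and the allocation workflow (Appendix E) is not shown. With tooth-by-tooth codes there is no inflation (step 6). This stands, and it is why the point is conditional. Everything that is shown attaches the group to the patient, however, so a shared arm is the natural reading.

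Second, 4.5 leaves regression to a biostatistician, who could add a patient cluster with the tooth still as the record. That room exists, but the text does not ask for it, and 3.4.2.3 points the other way.

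Third, the effect is small at the documented ratio. This also stands. Larger figures can be produced: alpha of 5.4% to 8.2% with 10 two-tooth children among 60 teeth. That is about twice what 85 teeth in 78 patients implies, and the top value also needs a correlation of 0.8. The documents do not support it as the expected case.

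A reader might also infer that analysing everything by tooth means that a child's questionnaire ratings are entered once per tooth. Section 3.4.2.3 collects these ratings from patients at each session, and no rule says to duplicate them, so that reading is not supported.

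**Conclusion.** The point holds in conditional form. The protocol allocates by patient, permits several teeth per child, and directs that each tooth count as an individual case regardless of patient. If a child's teeth share the arm and correlate positively, the correct standard error is about 1% to 6% larger than the planned one and the true alpha is about 5.2% to 6.5%; for correlations up to 0.5, alpha is at most about 6.0%. If 30 per group means teeth, power falls from 81.5% to about 81% to 76%, and it is already below the stated 80% at a correlation of 0.3.

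This rests on three assumptions: the shared arm, the retrospective ratio with extra teeth in pairs, and the range of correlations. The retrospective series included 13.9% incisors, whereas 3.4.1 specifies premolars, so the ratio may not carry over exactly.

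It would go too far to say that the standard errors are certainly wrong or that the trial's conclusions are unsafe. The error is modest, tends towards false positives, and is cheap to remove. It should be corrected.

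**What to change.** - **4.2:** state that all teeth of one child take the arm assigned to that child.
- **3.4.2.3 and 4.5:** keep the tooth as the record, but remove the clause in 3.4.2.3 that sets the patient aside and amend the individual-case wording in both places. Possible text: *Tooth-level outcomes will be analysed with patient as the cluster, using cluster-robust standard errors (or GEE) with a small-sample correction and a t reference on the number of patients minus 2 degrees of freedom.*
- **Mixed model:** a random-intercept model is an acceptable alternative only once the shared-arm rule is in 4.2. It does not hold its error rate if teeth of one child are allocated separately.
- **3.5:** say whether 30 per group means teeth or patients. If teeth, restate the power as about 81% to 76% under the stated assumptions, in place of the independent-teeth figure. If patients, that power loss does not arise.

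The cost is about one sentence in each of these sections and no new data. The downside is slightly wider intervals, about 1% to 6% at the assumed ratio and correlations, which are the correct ones.
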